## **9. TOLERABILITY VARIABLES AND ANALYSIS**

Injection site reaction adverse events will be listed and summarized descriptively. See Section [8.3](#).

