## 7.9. Assessment of Local Tolerability and Pain

Injection site assessments will be performed immediately (+10 minutes) and 1 hour (±15 minutes) after administration of each dose of the IMP (Table 1). The injection sites will be assessed for erythema, induration, and ecchymosis.

Severity will be graded according to the following criteria:

- Injection-site erythema, induration, and ecchymosis will be graded according to measurements: absent, 5 to ≤50 mm (mild), >50 to ≤100 mm (moderate), and >100 mm (severe). Induration must be assessed by careful superficial palpation, avoiding pressuring or squeezing the injection site.
- Spontaneous report of local pain after the injection will be measured as described in Table 4.

**Table 4:** Severity of Pain Scale for Injection Site Assessments

Symptom	Severity grade	Assessment
Pain	0	Absent
	1	Mild
	2	Moderate
	3	Severe

If a patient has severe injection site erythema, induration, ecchymosis, or pain at 1 hour after completion of IMP administration, the patient will be reassessed at 3 hours (±15 minutes) after completion of IMP administration and hourly (±15 minutes) thereafter, until the reaction is of moderate or less severity.

Appropriate treatment may be provided if necessary, in which case it must be recorded as concomitant medication.

Injection site reactions (injection site erythema, induration, ecchymosis, and pain) should be recorded as adverse events as described in Section 7.1.

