### 9.8. Tolerability Analysis

Injection site reaction assessments will be listed and summarized descriptively.

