### 1.3. Safety Endpoints

The safety and tolerability endpoints are as follows:

- occurrence of adverse events during the study
- clinically significant changes in physical examinations, including body weight

Statistical Analysis Plan

- clinical laboratory (serum chemistry, hematology and coagulation, and urinalysis) test results at each visit
- vital signs (blood pressure, respiratory rate, body temperature, and pulse) measurements at each visit  
Note: Oxygen saturation and respiratory rate will be measured in cases of suspected anaphylaxis and severe hypersensitivity.
- 12-lead electrocardiogram (ECG) findings at each visit
- use of concomitant medication during the study
- number (%) of patients who did not complete the study (day 168, end of study)
- number (%) of patients who did not complete the study due to adverse events
- local tolerability at the injection site (ie, erythema, induration, ecchymosis, and pain) at the following time points postdose: day 0, day 28, and day 56
- hypersensitivity reaction assessment
- Columbia Suicide Severity Rating Scale (C-SSRS)

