## 8. SAFETY ANALYSIS

### 8.1. General

For double-blind treatment period (up to visit 5), the safety analysis set will be used for all safety analyses. Summaries will be presented using descriptive statistics by treatment group as actually received unless otherwise stated and overall.

For open-label treatment period (visits 5 to 8/EOT/EOS/ET), OL-ITT analysis set will be used for safety analyses. Changes from baseline or change from visit 5 will be presented. Summaries will be presented using descriptive statistics overall. **The data will be analyzed after the completion of the study.**

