### 8.2. Duration of Exposure to Study Drug

#### 8.2.1. Double-Blind Treatment Period

During the double-blind treatment period patients will receive 3 sc injections of fremanezumab or placebo at visit 2, visit 3, and visit 4.

Duration of the double-blind treatment period (days) for a patient is defined as the number of days a patient is in the double-blind treatment period and calculated as the date of visit 5 - the first date of the IMP + 1. For patients who do not complete double-blind treatment period, date of visit 5 will be estimated as the date of last IMP administration in double-blind treatment period + 27. Dosing visit interval (days) is defined as the number of days between dosing visit (dose 1 and dose 2; dose 2 and dose 3) and calculated as date of next dosing - date of current dosing.

Duration of the double-blind treatment period (days), dosing visit interval (days), the number of doses received, and total number of injections received will be summarized using descriptive statistics. Summary will be presented by treatment group.

IMP administration and accountability data will be listed.

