### **8.3. Adverse Events**

Adverse events will be recorded from time informed consent is obtained through the end of study participation.

The following are considered protocol-defined adverse events of special interest (PDAESI) to be sent to the sponsor's Global Patient Safety and Pharmacovigilance Department for evaluation: ophthalmic-related adverse events of at least moderate severity, events of possible drug-induced liver injury (AST or ALT  $\geq 3 \times$  ULN, total bilirubin  $\geq 2 \times$  ULN, or international normalized ratio  $> 1.5$ ), Hy's Law events, or events of anaphylaxis and severe hypersensitivity.

All adverse events will be coded using MedDRA. Each patient will be counted only once in each preferred term or SOC category for the analyses of safety. Summaries will be presented for all adverse events (overall and by severity), adverse events determined by the investigator to be related to test IMP (defined as related or with missing relationship) (overall, overall by severity, serious AEs, PDAESI), serious adverse events, PDAESI, and adverse events causing withdrawal from the study. Adverse events with the missing flag indicating serious will be excluded from the summary of serious adverse events but included in the summary of non-serious adverse events.

Summaries for injection site adverse events will be presented (overall and by severity).

Listings for deaths, serious adverse events, adverse events leading to treatment withdrawn, adverse events leading to study discontinuation, adverse event requiring concomitant or additional treatment, injection site adverse events, PDAESI, and hypersensitivity and suspected anaphylaxis/hypersensitivity reactions related adverse events will be presented. In addition, listings for MedDRA dictionary terms for adverse event descriptions and adverse event preferred terms by patient number and treatment group will be presented.

Spontaneous abortion or an elective abortion due to developmental anomalies will be reported as a serious adverse event (protocol Section 7.2). These serious adverse events will be listed separately if applicable.

Summaries will include treatment-emergent adverse events which are defined as adverse events occurring at or after the first dose of the IMP. The listing will include all adverse events recorded.

Adverse events for patients who did not meet screening criteria will be listed.

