### **8.4. Injection Site Assessments**

Injection site assessments will be performed immediately (+10 minute) and 1 hour ( $\pm 15$  minutes) after receiving each dose of the IMP at visits 2, 3, and 4. The injection sites will be assessed for erythema, induration, and ecchymosis. More details are in Section 7.9 of the study protocol.

Injection-site reactions should be recorded as adverse events. Injection-site related adverse events will be summary as indicated in Section 8.3.

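### The SAP keeps local tolerability at days 0, 28 and 56 as an endpoint but plans only adverse-event summaries for it, and it leaves open which period same-day events at visit 5 belong to

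*SAP*

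**What the plan says.** **Endpoint.** SAP 1.3 lists, in the same terms as the protocol's objectives table, "local tolerability at the injection site (ie, erythema, induration, ecchymosis, and pain) at the following time points postdose: day 0, day 28, and day 56".

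**Collection.** Protocol 7.9 has the sites read immediately and at 1 hour after each dose, with size-based grades for erythema, induration and ecchymosis and a 0 to 3 scale for pain. SAP 8.4 repeats the schedule as "after receiving each dose of the IMP at visits 2, 3, and 4". It names the three visible signs but not pain, and refers to Protocol 7.9 for detail.

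**Analysis.** Protocol 9.8: "Injection site reaction assessments will be listed and summarized descriptively". SAP 9: "Injection site reaction adverse events will be listed and summarized descriptively", with a pointer to SAP 8.3. The only output that SAP 8.4 names is also the adverse-event summary in 8.3. SAP 17, on changes from the protocol, records none. The SAP Introduction says that the SAP prevails where the two documents differ.

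**Windows.** SAP 8.1: "For double-blind treatment period (up to visit 5), the safety analysis set will be used for all safety analyses". The same section gives open-label safety the range from visit 5 to visit 8. SAP 8.3 bases its summaries on treatment-emergent events, "defined as adverse events occurring at or after the first dose of the IMP", and states no end for either period. SAP 2.5.2 says that double-blind endpoints use data up to visit 5, and that data from the open-label period, visit 5 onward, are analysed separately.

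**The concern.** An endpoint defined by dose day has no planned summary by dose day. If the SAP is followed as written, the study report will contain injection-site adverse events but no table showing how local reactions looked after the first, second and third blinded doses in each arm. A reader of SAP 17 would not learn that the protocol's summary of the assessments had been replaced.

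The second issue bears on the table that remains. Every patient who continues into the open-label period receives fremanezumab at visit 5, and for a placebo patient this is the first exposure. Protocol 1.3.1 describes administration-site reactions as the most common treatment-emergent events with this drug. The adverse-event summary therefore needs a clear rule for events on the visit 5 date, and the SAP gives none.

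**Working it through.** The plan states no figure on this point, so the check sets the texts side by side and adds one count.

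**Part 1: dose day**

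1. Structure of the endpoint (SAP 1.3): 4 signs × 3 dose days = 12 sign-by-day summaries per arm. If the two routine readings in Protocol 7.9 are shown as well, 12 × 2 = 24.
2. Structure of the planned output (SAP 8.3): each patient is counted once in each preferred term. Assuming that each sign is coded to one preferred term, this gives 4 rows per arm, each also cut by severity. Dose day does not appear.
3. Example: patient X has mild erythema after all three blinded doses, and patient Y after the first only. By day 0/28/56, X contributes 1, 1, 1 and Y contributes 1, 0, 0. In the adverse-event table both contribute 1, so the summary cannot recover the pattern. The listing would allow a reader to infer the dose from onset dates patient by patient, but that is not a summary by day.
4. What is kept: Protocol 7.9 requires the four reactions to be recorded as adverse events, Protocol 7.1.3 sends their severity grading to 7.9, and SAP 8.3 summarises injection-site events overall and by severity. Sign and severity by arm therefore survive.
5. For comparison, SAP 8.8, 8.10 and 8.11 give explicit by-visit summaries for laboratory tests, vital signs and ECG. Local tolerability is also defined by visit and has no such summary.

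**Part 2: visit 5**

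1. SAP 8.1 puts visit 5 at the end of one safety window and at the start of the other. The footnote to SAP Table 1 (Section 4.4) says the same of the visit itself.
2. Open-label fremanezumab is given at visit 5 (SAP 2.1). Injection-site checks and a postdose adverse-event inquiry follow on the same day (Protocol Table 1 and Appendix H).
3. Such an event satisfies the treatment-emergent definition in SAP 8.3, which has a start and no end.
4. Double-blind columns follow the treatment received in the double-blind period (SAP 3.3). The separate group in that section covers only placebo patients given fremanezumab in error, so it does not catch planned dosing at visit 5.
5. The double-blind lock follows completion of visit 5 by the last patient (SAP 2.5.2), so these events can already be in the locked data.
6. Protocol 7.1.2 asks for onset and end dates, with duration for events under 24 hours, and states no onset clock time. A date alone does not separate predose from postdose events on that day. The separate predose and postdose inquiries do.

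A postdose reaction at visit 5 can therefore be tabulated in the double-blind columns. No text says that it will be.

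**The case against.** **The endpoint is largely reported anyway.** The reactions are recorded as adverse events with the 7.9 grades and are summarised by severity. This stands as far as it goes: it is too strong to say that the endpoint goes unreported. What is missing is the breakdown by dose day, which is how the endpoint is defined.

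**Protocol 9.8 does not prescribe a layout.** Correct. It asks only for a descriptive listing and summary. The dose days come from the endpoint in SAP 1.3. The immediate and 1-hour readings are part of the assessment schedule, so showing them separately is a preference rather than something the protocol requires.

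**The visit 5 boundary is already settled.** SAP 2.5.2 sends open-label data from visit 5 onward to a separate analysis, the notes in SAP 6.1.3 say that no blinded dose is given at visit 5, and SAP 8.4 confines its description to visits 2, 3 and 4. The duration formula in SAP 8.2.1, "calculated as the date of visit 5 - the first date of the IMP + 1", counts the visit 5 date but measures time in the period and does not attribute events. This is a reasonable reading and may well be the intention. But SAP 2.5.2 also includes data up to visit 5 in the double-blind analysis, and no section gives a predose/postdose rule for that date.

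**A stronger inference to avoid.** A reader might conclude that fremanezumab reactions will be added to placebo and that the arm comparison is biased toward no difference by a calculable amount. The documents do not support this. Misallocation is possible, not stated. Both arms receive fremanezumab at visit 5, so both columns would gain events, and a rise in the placebo rate is not the change in the arm difference. The documents give no injection-site rate for either arm, no onset timing for these reactions, and no count of placebo patients dosed at visit 5. The open-label period was added by Amendment 01, when 70 of the eventual 87 patients had been randomized, so that count cannot be taken as the whole placebo arm.

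**Conclusion.** The mismatch in Part 1 is established from the text and depends on no assumed rate. SAP 8.4 and 9 specify no listing or summary of the assessments, the SAP governs, and SAP 17 does not declare the difference. The loss is partial: sign and severity are kept, the day 0/28/56 structure is not.

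Part 2 is an ambiguity in the SAP that leaves room for error. Its effect on either column cannot be sized from the documents and would be near zero if few reactions follow the visit 5 dose.

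Both parts concern descriptive safety reporting only. They should be corrected because the correction is easy, but nothing here touches the primary or secondary efficacy analyses. The conclusion assumes that the graded assessments were captured as Protocol 7.9 requires; the case report form is not among the documents.

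**What to change.** 1. **SAP 8.4 and 9.** List and tabulate the collected graded assessments by sign (including pain), grade and dose day (0, 28, 56), by arm, preferably also by the Protocol 7.9 time points (immediate and 1 hour). Keep the adverse-event summary as support. If the sponsor prefers adverse events alone, SAP 17 should declare that departure from Protocol 9.8.
2. **SAP 8.1 and 8.3.** State that double-blind treatment-emergent events end immediately before the open-label dose at visit 5 for patients who receive it, and that open-label events start at that dose. Use the predose and postdose inquiries to place events with onset on the visit 5 date, and give a default for those that cannot be placed. For example, injection-site events dated that day could go to open label, since no blinded injection is given then.

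Cost: SAP wording, one further descriptive table and listing, and a cut-off rule in the adverse-event derivation. No new data collection.

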## **10. PHARMACOKINETIC ANALYSIS**

Pharmacokinetic plasma concentration results for fremanezumab will be tabulated descriptively at each planned sampling time point. The summary will be based on the safety analysis set. At the open-label period, pharmacokinetic plasma concentration results will be tabulated descriptively at each planned sampling time point per treatment group. The plasma concentration will be listed by scheduled visits, time points and treatment.

## **11. PHARMACOGENOMIC ANALYSIS**

Pharmacogenomic analysis will be conducted to correlate clinical observations (pharmacokinetic, safety, efficacy, or other effects) with genotypes observed in the study. Pharmacogenomic analysis may be conducted at a later time and will be reported in a separate addendum report.

## **12. PHARMACOKINETIC/PHARMACODYNAMIC ANALYSIS**

The pharmacokinetic/pharmacodynamic relationship analysis if performed will be reported separately.

**13. BIOMARKER ANALYSIS**

[REDACTED]

#### **14. IMMUNOGENICITY ANALYSIS**

A summary of immunogenicity results will be provided, and the incidence of immunogenicity will be calculated. The impact of immunogenicity on the pharmacokinetic profile, fremanezumab efficacy, and clinical safety will be evaluated.

## **15. PLANNED INTERIM ANALYSIS**

There will be no formal interim analysis. However, a database lock from the double-blind period will occur following the completion of visit 5 by the last patient. Unblinding will occur after the database lock from the double-blind period.

## **16. STATISTICAL SOFTWARE**

All data listings, summaries, and statistical analyses will be generated using SAS® version 9.4 or later.

**17. CHANGES TO ANALYSES SPECIFIED IN THE STUDY  
PROTOCOL**

None.

